## 1. Introduction

### 1.1 Study Foundation

Breast cancer claims 40-250% more African-American lives compared to White and Asian-Americans and is the most frequent cause of cancer deaths in Hispanics/Latinas. Breast cancer is diagnosed at later stages in African-Americans and Latinas suggesting persistent disparities in care delivery by race/ethnicity. Participation in clinical trials by women of color (WOC, which is defined as non-white women for the purposes of this study) is needed to improve outcomes, reduce health inequity and increase trial generalizability. Disappointingly, within ECOG-ACRIN, WOC participation remains less than 10% regardless of trial type (therapeutic, diagnostic/ surveillance or screening). Improving clinical trial participation among WOC is therefore a high priority to ensure that trial results are truly generalizable to women of all racial/ethnic groups.

### 1.2 Background

In EA1151 Tomosynthesis Mammographic Imaging Screening Trial (TMIST), a randomized controlled trial of digital mammography (DM) vs tomosynthesis (TM) to evaluate stage shift in screen-detected cancers, participation by Asians and Hispanics in particular have lagged. Cost concerns are a known barrier to trial participation disproportionately affecting WOC. The COVID-19 pandemic will likely worsen trial participation among WOC. Unfortunately for many women, participation in TMIST can result in out-of-pocket costs since commercial insurance coverage of TM is widely variable. Concerns about study-related costs are a known barrier to trial participation and the COVID-19 pandemic has resulted in record unemployment and insurance loss that has disproportionately affected minorities.

The economic toll can be broadly considered as financial hardship which has two main components, 1) material condition referring to actual financial resources available, and 2) psychological response to their material condition (see model). This financial hardship will further constrain many participants' financial resources (material condition) and ability to afford out-of-pocket expenses associated with trial participation and may lead to financial distress (representing the psychological response), preferentially affecting WOC who decline participation compared to non-WOC who decline. Additional federal-, state- and local-level factors (e.g., shelter-in-place policies, local unemployment during COVID-19) may also contribute to trial nonparticipation (Fig 1). COVID-19 is a natural experiment to compare the role of financial hardship on willingness to participate in clinical trials between WOC and non-WOC and any widening of disparities in WOC trial participation in TMIST. This observational ancillary study results will be used to inform future trials of interventions to improve trial participation among WOC, e.g., financial assistance and financial navigation services for trial-related expenses.

In a population of women who decline participation in TMIST (EAQ201 participants), we plan to compare the proportion of WOC who experience COVID-related change in their material condition (income/employment/insurance loss) vs non-WOC. Secondary and exploratory analyses will compare the proportions of WOC vs non-WOC with other person-level COVID-related factors

(including distress and fear of exposure during medical care) and assess federal-, state- or local-level COVID-related factors (e.g., state infection rates and shelter-in-place policies and local-level unemployment during shelter-in-place) as moderators. We hypothesize that COVID-19 related financial hardship and distress are more prevalent in WOC who decline TMIST participation compared to non-WOC who decline participation.

[figure not shown]
We will compare the effects of sociodemographics, and federal-, state- or local-level COVID-19 factors on TMIST participation, in WOC vs non-WOC. We hypothesize that federal-, state- or local-level COVID-19 factors more severely affect participation among WOC after controlling for other sociodemographic factors at the person-level (e.g., insurance type, socioeconomic status (SES)).

Our conceptual model integrates components of a traditional health services/care delivery model, an emerging model of financial hardship effect on health, and a model of psychological distress and coping to provide an innovative multi-level perspective on the effects of COVID-19 on a unique outcome, screening trial nonparticipation. While other studies have evaluated person-level factors or region-level factors, few can integrate factors at the individual, provider/organization, federal and state level to comprehensively evaluate barriers to trial participation. Incorporating COVID-specific distress and financial distress in trial nonparticipation is also novel, and to date the impact of these factors, particularly among WOC, is completely unknown.

We previously demonstrated that imaging out-of-pocket (OOP) costs cause worry among 36% of outpatients undergoing CT/MRI at UMICHIGAN out-patient imaging clinics. Those with ACA marketplace insurance were twice as likely to report worry over OOP costs of the test (OR 2.0, 95%CI 1.1, 3.5) compared to those with employer-sponsored insurance. 10% reported nonadherence to recommended care over the last 3 months such as declining a test or skipping or taking less medication than prescribed because of cost. Participants who worry about OOP costs were more likely to report nonadherence by 5-fold (OR 5.7, 95%CI 3.3, 9.8) than that those who did not. We hypothesize that when approached to participate for an imaging trial such as TMIST, women with existing OOP concerns or less generous insurance plans are more likely to decline participation than those who do not have existing OOP concerns or more generous insurance plans.

We have successfully used a combination of paper and online survey administration and data collection in EAQ162CD, a longitudinal observational study of financial hardship in early stage colorectal cancer and two imaging trials that collected patient reported outcomes, E4112 Prospective Study of MRI and Multiparametric Expression Assay in Ductal Carcinoma in Situ and EA1141 Comparison of Abbreviated Breast MRI and Digital Breast Tomosynthesis in Breast Cancer Screening in Women with Dense Breasts. Depending on the study, 47-78% of women opted for online surveys. We have developed email and telephone reminders (see Section [4.3.5](#)) for timely survey completion and processes for collecting any missing information.

Fig 1: Model of COVID effects on health

## 2. Objectives

### 2.1 Primary Objectives

2.1.1 In a population of women who decline participation in TMIST (EAQ201 participants), we will compare the proportion of WOC vs non-WOC with respect to who experience COVID-related financial hardship, a composite endpoint defined as any psychological response (financial distress, food/housing insecurity) or change in their material condition.

### 2.2 Secondary Objectives

2.2.1 Compare the proportions of WOC vs non-WOC EAQ201 participants with COVID-related change in their material condition, a composite measure.

2.2.2 Compare the proportions of WOC vs non-WOC EAQ201 participants with COVID-specific perceived financial distress.

2.2.3 Compare the proportion of WOC in TMIST participants vs EAQ201 participants. A key hypothesis (now 2.2.3) is that financial hardship preferentially affects WOC and therefore their participation in TMIST. In order, to test this hypothesis, we need to compare the proportion of WOC who participated in TMIST compared to those who declined to participate in TMIST (estimated by EAQ201 participants).

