EAQ201 project manager will create a list of eligible sites based on EA1151 recruitment and enrollment status and will notify CTSU of ECOG-ACRIN clearance of this site qualification criteria. Site submission of required IRB documentation to NCI CIRB will be monitored in RSS weekly by the EAQ201 project manager who will report site activation clearances in CTSU weekly to the EAQ201 study chair by [define weekly communication mechanism you prefer here]. All sites that plan to open EAQ201 are strongly encouraged to activate EAQ201 within 30 days of ECOG-ACRIN activation of the trial as there will be no maximum number of subjects that can be enrolled in the trial at any one site and enrollment is expected to be completed within a few months.

EAQ201 project manager will reach out weekly to all eligible EA1151 sites to remind them about the EAQ201 study and obtain IRB approval through NCI CIRB. This outreach will occur by email to TMIST PI and TMIST lead coordinator until the site opens EAQ201, declines to participate, or EAQ201 enrollment reaches 50% of planned enrollment, 500.

**Participant Recruitment Plan:** All participating EAQ201 TMIST sites will be expected to approach at least 20 women per month in person or over the phone as part of their TMIST recruitment effort while EAQ201 is open to participant enrollment with at least 5 women approached that are classified as Women of Color [definition] according to information documented in the site's electronic medical record system.

All women presenting for screening mammography who meet the eligibility criteria for EA1151 but ultimately decline to participate in EA1151 should be immediately invited to participate in EAQ201 by EA1151 site designated recruiters.

All EAQ201 TMIST sites are expected to keep local TMIST recruitment logs for duration of EAQ201 enrollment period. The first two weeks of local TMIST recruitment logs for each site are to be submitted to the EAQ201 project manager to confirm that recruitment effort is happening for TMIST and to monitor number of WOC TMIST declines at the site. This information will be summarized across all sites for reporting to the EAQ201 central trial team to compare to EAQ201 enrollment rates at each site to determine if site is on track to complete within timeline planned and that overall WOC versus non-WOC participation ratio is within 10%-25% range planned.

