#### 7.1.2 Secondary Objectives

7.1.2.1 Compare the proportions of WOC vs non-WOC EAQ201 participants with COVID-related change in their material condition, a composite measure.

Hypothesis: Compared to non-WOC, WOC will experience more COVID-related change in their material condition.

7.1.2.2 Compare the proportions of WOC vs non-WOC EAQ201 participants with COVID-specific perceived financial distress.

Hypothesis: Compared to non-WOC, WOC will experience more COVID-specific perceived financial distress.

7.1.2.3 Compare the proportion of WOC in TMIST participants vs EAQ201 participants.

Hypothesis: The proportion of WOC should be higher in the TMIST decliners than that in TMIST agree-ers.

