7.2 Primary Objective

The primary objective is to compare the proportion of WOC EAQ201 participants who experience COVID-related financial hardship vs non-WOC EAQ201 participants. The results, with and without adjustment for missing values (see [7.5](#)), will be compared as a sensitivity analysis. Logistic regression models, with and without stratification by WOC status, will be fit with financial hardship as the response variable to investigate other sociodemographics (e.g., age, marital status, insurance status) and state- and local-level factors (e.g., state COVID severity, shelter-in-place policies, state and local unemployment during shelter-in-place) as moderators.

Sample Size Considerations for the Primary Objective ([7.1.1](#)):

The primary objective is to compare the proportion of WOC EAQ201 participants who experience COVID-related financial hardship (see **Table 1** for definition) with the proportion of non-WOC EAQ201 participants who experience COVID-related financial hardship. The National Bureau of Economic Research estimated unemployment rates by race and ethnicity in April 2020, around shelter-in-place regulations. Unemployment in African-American and Latinx populations averaged 18% compared to Whites (13%). At a sample size of 1000 women who decline TMIST participation, we expect to recruit at least 10-25% WOC into this study. Assuming alpha of 0.05, we estimated power over a range of differences across various proportions (see **Table 4**). For instance, at a sample size of 1000 with 10% of WOC, we have 77% power to detect a minimum difference of 0.10 between two proportions (0.2 vs. 0.1); at a sample size of 1000 with 25% of WOC, we have 88% power to detect a minimum difference of 0.08 between two proportions (0.18 vs. 0.1). Please note that based on DCP-001, 16% of the women who declined TMIST were WOC. Accrual onto TMIST is expected to continue for another 4.4 years. Also based on DCP-001 and extrapolating to the Non-NCORP US sites, accruing 1,000 women to this study is achievable. We do not envision any danger that this study will close due to lack of accrual.

**Table 4: Estimated power for a two-sample proportions using Fisher's Exact test (two-sided). N1: # of WOC; N2: # of non-WOC**

Sample size (N)	N1/N2	P1 (WOC)	P2 (non-WOC)	Delta	Alpha	Power
(Sample size: 1000; N1/N2=1/9, i.e.,10% of WOC)						
1000	1/9	0.200	0.100	0.100	0.05	0.77
1000	1/9	0.225	0.100	0.125	0.05	0.90
1000	1/9	0.250	0.100	0.150	0.05	0.96

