### 7.3 Secondary Objectives

Two-sample proportion tests (e.g., Z-test based on normal approximations or Fisher's exact test) will be used to compare the proportions of WOC vs non-WOC EAQ201 participants with 1) COVID-related change in their material condition; 2) COVID-specific perceived financial distress. Logistic regressions may be performed to adjust for potential confounders during the comparisons. Missing data will be managed as below (See [7.5](#)).

The proportion of WOC in EAQ201 participants will be compared to the proportion of WOC in TMIST participants using the one-sample proportion test. Based on the TMIST data, the proportion of WOC in TMIST participants is around 25%. Then we will have 80% power to detect a difference of 3.9% using a two-sided exact test with a significant level of 0.05.

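### Objective 2.2.3 takes the WOC share of all TMIST decliners from those who then join EAQ201, and the analysis does not correct for uptake that may differ by WOC status

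*Combined protocol and SAP*

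**What the plan says.** Section 2.2.3 calls this a key hypothesis. It asks for the WOC share of TMIST participants against the share of "those who declined to participate in TMIST (estimated by EAQ201 participants". Section 7.1.2.3 gives the direction: "The proportion of WOC should be higher in the TMIST decliners than that in TMIST agree-ers".

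Section 7.3 gives the analysis: "The proportion of WOC in EAQ201 participants will be compared to the proportion of WOC in TMIST participants using the one-sample proportion test". The reference comes from TMIST data, in which "the proportion of WOC in TMIST participants is around 25"%, and the section claims 80% power for a 3.9-point difference with a two-sided exact test at 0.05.

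The route into EAQ201 is set out in Sections 3.1 and 5. A woman must have been eligible for TMIST and declined it, be able to complete questionnaires in English, be asked separately about EAQ201, and sign a paper consent.

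Section 5 also describes recruitment and monitoring. Sites are to approach at least 20 women a month for TMIST, "with at least 5 women approached that are classified as Women of Color". The central team checks that the "overall WOC versus non-WOC participation ratio is within 10%-25% range planned". Sites keep TMIST recruitment logs throughout EAQ201 enrolment, but "The first two weeks of local TMIST recruitment logs for each site are to be submitted" centrally. Section 7.2 adds that, "based on DCP-001, 16% of the women who declined TMIST were WOC".

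**The concern.** The quantity wanted is the WOC share of all women who declined TMIST. The quantity measured is the WOC share of decliners who said yes to something else. The two agree only if WOC and non-WOC decliners take up EAQ201 at the same rate. Nothing in the plan measures that rate by WOC status over the enrolment period, and nothing in 7.3 adjusts for it. Section 7.5 deals with attrition among women already enrolled, not with decliners who refuse EAQ201.

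Unequal uptake is plausible on the plan's own reasoning. Section 7.5 allows that women lost to follow-up may carry more financial burden, and Section 1.2 hypothesises that hardship is more common among WOC decliners. If uptake does differ, the test can report that WOC are over- or under-represented among decliners when TMIST refusal does not differ, or it can hide a real difference. Either result would feed into the financial-assistance interventions that Section 1.2 says this study is meant to inform.

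**Working it through.** **Inputs.** Reference share p0 = 0.25, two-sided exact test, alpha 0.05, difference 3.9 points (7.3); n = 1,000 (7.2); WOC share of decliners 16% from DCP-001 (7.2); monitored range 10-25% (Section 5). Relative uptake r (EAQ201 uptake in WOC decliners divided by uptake in non-WOC decliners) is not in the documents and is varied as an assumption.

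**1. The plan's own figure.** With X ~ Binomial(1000, 0.25), the equal-tailed exact test rejects at X ≤ 222 (tail 0.0213) or X ≥ 278 (tail 0.0232), so its actual size is 4.5%. Power is 78.8% at a true 28.9% and 81.4% at 21.1%. The stated 80% for 3.9 points is reproduced. The arithmetic in 7.3 is sound; the issue is what is being estimated.

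**2. Effect of uptake.** If s is the true WOC share of decliners, the expected EAQ201 share is

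s·r / (s·r + 1 − s).

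With no true difference (s = 0.25), for example r = 0.8: 0.20 / (0.20 + 0.75) = 0.211.

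| r (assumed) | Expected EAQ201 share | Probability of rejection |
|---|---|---|
| 0.8 | 21.1% | 82% |
| 0.9 | 23.1% | 27% |
| 1.0 | 25.0% | 4.5% |
| 1.1 | 26.8% | 25% |
| 1.25 | 29.4% | 88% |

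The r that produces the whole design difference follows from the odds. Upward: (0.289/0.711) / (0.25/0.75) = 1.22. Downward: (0.211/0.789) / (0.25/0.75) = 0.80.

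**3. Masking a real difference.** With s = 0.289, r = (0.25/0.75) / (0.289/0.711) = 0.82 brings the expected share back to 25.0%. The probability of rejecting in the hypothesised direction falls from 79% at r = 1 to 24% at r = 0.9 and 1% at r = 0.8.

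**4. Planning range against hypothesis.** Significance in the hypothesised direction needs 278/1000 = 27.8% or more, which is above the top of the 10-25% range. An observed share of 22.2% or less, which covers most of that range, is significant in the opposite direction. Read literally as a ratio of WOC to non-WOC, the range is 0.10/1.10 = 9.1% to 0.25/1.25 = 20.0%, all of it in the lower rejection region. If the DCP-001 figure of 16% were the true decliner share, an EAQ201 share of 27.8% would need r = (0.278/0.722) / (0.16/0.84) = 2.02.

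**5. Comparator.** Section 5 mentions comparing sociodemographics with women who agree to TMIST over the same period. Section 7.3 does not refer to this. Selection of TMIST participants by site and enrolment time is specified only in 7.4, for exploratory objective 7.1.3.5.

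**The case against.** The proxy is openly disclosed in 2.2.3, the comparison is one secondary objective, and the primary objective does not depend on it. Every rejection rate above other than the equal-uptake one rests on an assumed r. Section 5 provides a same-period comparison, and Table 1 lists race/ethnicity among the TMIST items, so the 25% may be only a planning value. The two-week logs are summarised, including WOC declines, and set against EAQ201 enrolment at each site, which is a partial check on uptake. All of this stands. It limits the weight of the point but does not supply a correction: two weeks of logs used for monitoring do not enter the analysis, and a same-period comparator does nothing about the second opt-in.

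A reader might go further and infer that a WOC quota sets the EAQ201 share. The documents do not support that. The 5-of-20 figure is a floor on women approached for TMIST, before any of them accepts or declines, so it acts on both groups. Nor is the 10-25% range shown to control accrual: Section 5 states no cap or corrective action, and Section 7.2 words it as a minimum expectation.

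A reader might also infer that the TMIST group escapes every filter. Women who ignore written invitations enter neither group, and these documents do not give TMIST's language criteria. What clearly differs is the second consent and the restriction to EAQ201 sites.

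The proposed remedy has limits too. DCP-001 appears as a single figure without period, completeness or race definition. Log data would rest on race from the medical record, whereas EAQ201 race is supplied at registration.

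**Conclusion.** The concern holds in this form: differential EAQ201 uptake by WOC status is unmeasured over the enrolment period and uncorrected in the analysis of 2.2.3. A relative difference of about 20% in either direction is enough to create or erase the whole 3.9-point difference that 7.3 is powered to find. That statement is conditional on an assumed r, n = 1,000 and a reference fixed at 25%. The documents cannot show that uptake does differ, in which direction, or that EAQ201 recruitment weighs as heavily in the result as TMIST refusal.

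The monitored range, the DCP-001 figure and the hypothesis in 7.1.2.3 are mutually inconsistent as planning statements and need to be reconciled. It is tempting to read 16% against about 25% as showing that the hypothesis is already false. The two figures are not shown to share a period, site base or definition, so that does not follow.

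This is worth correcting before analysis, but it does not affect the validity of the primary comparison.

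**What to change.** Have sites submit full-period counts from the TMIST recruitment logs they already keep, in place of the first two weeks only: women eligible and approached, accepted and declined, each by WOC status. Base 2.2.3 on TMIST acceptance in WOC against non-WOC at the same sites and in the same months, with race from one source (the medical record) for both groups. The approach floor acts before the accept-or-decline decision, so it does not bias that comparison.

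Report EAQ201 uptake among decliners by WOC status, and present the EAQ201 WOC share as a description of the sample. Reconcile the 10-25% range and the 16% figure with the hypothesis in 7.1.2.3.

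If full-period logs cannot be obtained, reword 2.2.3 and 7.1.2.3 to describe EAQ201 participants rather than all TMIST decliners, and show how the result changes over a range of relative uptake.

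The cost is a short protocol change as well as analysis wording, modest site paperwork in a study with limited supplement scope, and reliance on race as recorded in the medical record.

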### 2.3 Exploratory Objectives

2.3.1 Compare the proportion of WOC vs non-WOC EAQ201 participants with COVID-related employment change, a composite measure.

2.3.2 Compare the proportions of WOC vs non-WOC EAQ201 participants with COVID-specific perceived distress and perceived susceptibility to COVID and breast cancer.

2.3.3 Compare the proportions of WOC vs non-WOC EAQ201 participants with relative increase in smoking and alcohol use, risk factors for breast cancer.

2.3.4 Compare participant-reported quality of life, anxiety and depression between WOC and non-WOC EAQ201 participants.

2.3.5 Assess the effects of sociodemographic characteristics, and federal-, state- or local-level COVID-19 factors on TMIST participation, in WOC vs non-WOC.

Rev. Add2 **3. Selection of Sites**

All interested NCORP and the three selected non-NCORP TMIST sites located in the United States will be invited to participate. There will be no specific exclusion criteria (i.e., minimum number of cases) because we would like to include a wide variety of different systems to better understand the variability in available financial resources and participant experiences.

